**Difference in amputation rates: Control group minus HBOT**

[figure not shown]

Figure 2 Possible scenarios at the interim analysis

## 5. TREATMENT OF SUBJECTS

### 5.1 Investigational product/treatment

Patients allocated to the intervention group will receive 20, 30 or 40 sessions of HBOT adjunctive to standard care, as determined by the randomisation. A HBOT session will take 90 to 120 minutes at 2.2-2.5 ATA. Besides the 90-120 minutes of treatment, approximately 20 minutes are required for compression and decompression. During the treatment session the patients will breathe 100% FiO2 except for 3 blocks of 5 minutes during which atmospheric air will be administered to prevent oxygen intoxication. This HBOT-regimen has been approved by the hyperbaric medicine specialists from all contributing HBOT-centers as the optimum and safest HBOT procedure for these patients. Patients will either lay in bed or sit in a chair during the session. At least for the first time, cabin personnel will accompany patients in the cabin and instruct them about the use of the oxygen masks or hoods. The cabin will be pressurized gradually in about 10 minutes. Subsequently, the supervising staff member will supply patients with masks through which the oxygen will be administered. The staff member will then leave the cabin, but will remain in constant contact with the patients through cameras and microphones. In case of adverse events requiring termination of the session, patients will be able to leave the cabin after a short decompression period. After the treatment, the cabin will be decompressed in about 10 minutes.

HBOT will be administered in a hyperbaric chamber. HBOT is preferably given 5 times per week, but at least 3 times per week, until the total number of sessions has been reached. To minimize interruption of HBOT and masking of the effect by additional vascular interventions, any (additional) (endo)vascular procedure will preferably be performed after randomisation but before the start of HBOT treatment. In case a vascular intervention is required (due to progression of the disease) while the patient is undergoing the HBOT sessions, these are interrupted for the period of the vascular intervention and continued directly afterwards until completion of the sessions.

[figure not shown]

Figure 3 Example of HBOT tabel

**5.2 Use of co-intervention (if applicable)**

HBOT will be given in addition to standard care according to local best practice in expertise centers and will not intervene with the usual care. Although (vascular) interventions are preferably performed before the start of HBOT, participation in the study will not influence any additional interventions that might be needed during follow-up ((endo)vascular interventions, amputations, wound debridement, medication, etc).

**5.3 Escape medication (if applicable)**

Not applicable.

## **6. INVESTIGATIONAL PRODUCT**

### **6.1 Name and description of investigational product(s)**

In this trial, oxygen will be used under hyperbaric conditions. In addition, 100% oxygen will be administered. Both can be either cryogenic preserved oxygen or compressed oxygen.

### **6.2 Summary of findings from non-clinical studies**

For the scope of this study the finding in non-clinical studies are not relevant, since HBOT is already widely implemented in humans and clinical studies are available.

### **6.3 Summary of findings from clinical studies**

HBOT has a variety of mechanisms of action: it improves tissue oxygenation; inhibits the pro-inflammatory reaction by reducing cytokines; improves neo-vascularization; has a bacteriostatic effect on anaerobic bacteria and stimulates stem cells and growth factors (Camporesi 2014). There are 14 indications of HBOT approved by the UHMS, including the treatment of air or gas embolism, arterial insufficiencies, carbon monoxide poisoning and gas gangrene (Weaver 2014). Also see the attachments D1, page 1.

### **6.4 Summary of known and potential risks and benefits**

Risks: HBOT might cause middle ear and sinus barotrauma, myopia and epileptic seizures; see the structured risk analysis (see chapter 12).

Benefits: A recent meta-analysis (Brouwer 2020) shows evidence that HBOT can prevent major amputation in patients with ischemic DFUs.

### **6.5 Description and justification of route of administration and dosage**

Patients will undergo sessions of 90 to 120 minutes under 2.2-2.5 ATA according to international treatment standards (Weaver 2014). Usually every 20 minutes an air break will be implemented, where patients only breathe room air. This reduces the risks of oxygen toxicity. This falls within the limits of standard use of 1.4-3.0 ATA for 45 to 300 minutes (attachments D1, page 2).

### **6.6 Dosages, dosage modifications and method of administration**

Depending on local protocols, patients will breathe 90 to 120 minutes of HBOT under 2.2-2.5 ATA. The total number of sessions will vary between 20 and 40, depending on the randomisation.

**6.7 Preparation and labelling of Investigational Medicinal Product**

The oxygen has to be prepared and labelled according to the standard operation procedures of the AMC (attachment K6 SOP). All centers have to record the quality certificates of the oxygen used for patients included in the trial.

**6.8 Drug accountability**

The shipment, receipt, disposition, return and destruction of oxygen will not be affected by this study. All HBOT-centers already have to record the quality certificates of the oxygen used for patients included in the trial.

## 7. METHODS

### 7.1 Study parameters/endpoints

The effectiveness of HBOT will be calculated from three different perspectives: Wound-related, patient-related and society-related.

- Wound-related outcome measures include limb salvage (major amputation rate), minor amputation rate, amputation-free survival and (time to) complete ulcer healing.
- Patient-related outcomes measures will be measured by a common disease-specific questionnaire (Vascuqol), and a generic questionnaire (SF-12), and a pain score (VAS)
- From a societal perspective, outcomes relevant for the calculation of the cost-effectiveness, cost-utility and budget impact will be measured. (volumes and treatment costs, EQ-5D-5L questionnaire)

#### 7.1.1 Main study parameter/endpoint

- Major amputation rate (above ankle) and (major) amputation-free survival after 12 months of follow-up

#### 7.1.2 Secondary study parameters/endpoints (if applicable)

- Complete wound healing
- Time to reach complete wound healing
- Freedom from minor amputation (below ankle)
- Pain score (VAS)
- Health-related quality of life scores
  - EQ-5D-5L
  - SF-12
  - Vascuqol-6
- Costs related to HBOT and conventional therapy during follow-up period
- Patients' out of pocket expenses related to disease or treatment (travel expenses etc.)
- Mortality
- Patients' perception of improvement (through one anchor question)
- Forefoot TcpO2 before, during and after (HBOT) treatment (if equipment is available)

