### 7.3 Study procedures

Patients from each (remaining) study arm will be monitored up to 36 months after randomisation. At the start of the trial, patients' baseline characteristics will be obtained. Pain scores will be collected through first phase of the trial. Questionnaires will be completed at baseline and will be sent to the patients' home after 3 months and 1 year.

Amputation rate, ulcer recurrence, additional interventions, mortality, adverse events and costs will be monitored after 1 year and 3 years.

Assessment	Before randomisation	Week 1-8, once a week	After 3 months	After 1 year	After 3 years
Patient characteristics	*				
Meggitt-Wagner classification	*		*	*	
Wound measurements	*				
Ankle blood pressure	*		*	*	
Toe systolic pressure	*		*	*	
TcPO2	*		*	*	
VAS		*	*	*	
Freedom of amputation			*	*	*
Complete ulcer healing			*	*	*
Recurrent ulcer			*	*	*
Nr of additional vascular events		*	*	*	*
Adverse events		*	*	*	
Patient's out of pocket expenses			*		
Questionnaires	*		*	*	*

*Table 1 Assessments and follow-up*

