### 9.2 Secondary and other study parameters

Differences in (semi-)continuous variables between the two treatment groups (such as the VAS, TcpO2 and quality of life scores) will be analysed with the Student t-test in case of normally distributed data and otherwise the non-parametric Mann-Whitney U test, after correcting for baseline differences, if any.

Time to complete wound healing will be estimated using Kaplan-Meier survival analysis and differences between the groups will be analysed using the log-rank test. Changes over time of TcpO2 and quality of life scores will be analysed using the Wilcoxon test. Potential confounding factors will be adjusted using Cox proportional hazards regression modelling.

The economic evaluation of additional HBOT will be performed as a cost-effectiveness analysis from a societal perspective. Additionally, a cost-utility analysis will be performed with the costs per quality adjusted life-year (QALY) as outcome. As the time horizon is restricted to 12 months, no discounting (of costs and effects) will be performed.

The EQ-5D is used to generate health status scoring profiles over time, which will subsequently be translated in QALYs by applying time trade-off based health utility algorithms and assuming that interpolation between successive measurements best reflects a patient's health status during the year. Sensitivity analyses will be performed to account for sampling variability, for plausible ranges in unit costs, and for different health

utility algorithms. In addition, a budget impact analysis will be undertaken to assess the possible cost savings of HBOT if applied to all eligible patients on a national scale.

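### Out-of-pocket expenses feed a 12-month societal evaluation, but Table 1 schedules their collection only at 3 months, and the text of 7.3 does not settle whether they are collected later

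*Protocol*

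**What the plan says.** Protocol 7.1.2 lists two cost items among the secondary endpoints. One is "Costs related to HBOT and conventional therapy during follow-up period". The other, listed separately and without a time window, is patients' "out of pocket expenses related to disease or treatment (travel expenses etc.)".

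Protocol 9.2 says that the economic evaluation "will be performed as a cost-effectiveness analysis from a societal perspective", adds a cost-utility analysis with cost per QALY, and fixes the horizon: "As the time horizon is restricted to 12 months, no discounting (of costs and effects) will be performed".

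Protocol 7.3 deals with collection in two places:

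- The text says that "additional interventions, mortality, adverse events and costs will be monitored after 1 year and 3 years". It does not say which costs.
- Table 1 has a row "Patient's out of pocket expenses" with one mark, in the 3-month column. There is none at 1 year or 3 years, and the table has no general row for costs.

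On questionnaires, 7.3 says: "Questionnaires will be completed at baseline and will be sent to the patients' home after 3 months and 1 year".

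**The concern.** A societal evaluation counts what patients pay themselves. The endpoint covers expenses due to the disease as well as those due to treatment, so it should run over the same 12 months as the effects. As scheduled in Table 1, it runs over the first 3 months only.

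The recorded and unrecorded periods also differ in content. The first 3 months contain most of the travel to HBOT sessions. Months 4 to 12 contain whatever patients go on paying for wound care, later interventions or life after an amputation. A cut at 3 months may therefore affect the arms unequally.

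This belongs in the protocol because the protocol sets the collection schedule. An analysis plan cannot recover expenses that patients were never asked about.

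**Working it through.** The protocol states no figure for this point, so there is none to reproduce. The check compares the schedule with the horizon, and the length of an HBOT course with the collection window.

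**Inputs**
- Horizon: 12 months (9.2).
- Scheduled collection of out-of-pocket expenses: 3 months only (Table 1). No recall period is given; I assume that the item looks back to randomisation.
- Sessions: 20, 30 or 40 in the HBOT arms (section 3).
- Frequency: preferably 5 per week, at least 3 (5.1).
- Start of HBOT: 5.1 prefers any vascular procedure to fall between randomisation and the first session. It gives no length for this delay, so I assume 0, 2 and 4 weeks.
- 3 months = 365.25 / 12 × 3 / 7 = 13.04 weeks.

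**Share of the horizon covered**
- Covered: 3 / 12 = 25%.
- Not covered: (12 − 3) / 12 = 9 / 12 = 75%.

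**Course length = sessions / sessions per week**

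| Sessions | At 5 per week | At 3 per week |
|---|---|---|
| 20 | 4 weeks | 6.7 weeks |
| 30 | 6 weeks | 10 weeks |
| 40 | 8 weeks | 13.3 weeks |

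**Share of sessions completed by 3 months = min(sessions, (13.04 − delay) × frequency) / sessions**

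At 5 per week, every course is complete for every delay tried. At 3 per week:

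| Sessions | No delay | 2-week delay | 4-week delay |
|---|---|---|---|
| 20 | 100% | 100% | 100% |
| 30 | 100% | 100% | 90.4% |
| 40 | 97.8% | 82.8% | 67.8% |

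For example, 40 sessions with a 4-week delay: (13.04 − 4) × 3 = 27.1 sessions, and 27.1 / 40 = 67.8%.

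A single 3-month record thus captures all or nearly all HBOT travel, except for slow and delayed courses of 40 sessions and, to a lesser degree, of 30. With collection at 1 year added, covering the time since the 3-month questionnaire, the full 12 months would be covered.

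**The case against.** The strongest reply is that Table 1 is not a full list of what is collected. It has no row for mortality or for treatment costs, yet the text of 7.3 says that both are monitored after 1 year and 3 years. A missing mark is therefore weak proof that nothing is asked at 1 year. This stands in part. It rules out saying that the later expenses are certainly lost. But out-of-pocket expenses are the one cost item that Table 1 does name, and the table gives it a single time point. The general sentence about costs does not say that it includes them, and a site that works from the table would not ask.

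A second reply is that most later costs have an endpoint of their own, since treatment costs run over the whole follow-up. In addition, 7.1 does not name out-of-pocket expenses when it describes the societal inputs. This also stands in part: only the patient-paid component is at issue, and its use in the cost per QALY is inferred from the societal perspective and from its place among the endpoints.

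A reader might go further and infer that the incremental cost of HBOT will be overstated, most of all with 40 sessions. The documents do not support this:

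- The protocol gives no amounts for patient-paid costs.
- The direction depends on HBOT working and on what patients pay in months 4 to 12. Section 1 reports no effect of HBOT on minor amputation or complete healing in the meta-analysis, and a saved limb with an open ulcer may cost the patient more than an amputation.
- Section 9.3 expects most amputations within 3 months, so part of the related expense would be recorded.
- The 40-session arm is the one whose own travel is most likely to run past 3 months, which would understate its cost.

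**Conclusion.** The point holds as a mismatch between the schedule and the planned evaluation, and as a disagreement between text and table within 7.3. If Table 1 is followed, 9 of 12 months (75%) have no scheduled out-of-pocket data, and a cost per QALY would combine 3 months of patient-paid costs with 12 months of QALYs. The gap may differ between arms. Neither its size nor its direction can be computed from the protocol.

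This rests on the 3-month item looking back to randomisation, on these expenses entering the societal evaluation, and on the 1-year cost monitoring in 7.3 not already including them. If it does include them, what remains is an inconsistency to be corrected in Table 1. The matter should be put right in either case, because the correction is cheap and data that were not collected cannot be restored at the analysis.

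**What to change.** - In Table 1, mark out-of-pocket expenses at 1 year as well as at 3 months.
- State the recall periods: since randomisation for the 3-month item, and since the 3-month questionnaire for the 1-year item.
- Send the 1-year item with the questionnaires already planned for that time.
- Reword the cost sentence in 7.3 so that it names the cost items collected at each time and agrees with Table 1.

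The cost is a few extra questions in an existing mailing. The drawback is the longer recall at 1 year, about 9 months against 3, which makes the later item less precise.

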#### 7.1.3 Other study parameters (if applicable)

- Complications directly related to HBOT treatment (e.g. middle ear and sinus barotrauma, epileptic seizure, myopia)

### 7.2 Randomisation, blinding and treatment allocation

Randomisation will be performed through Castor Electronic Data Capture (Amsterdam, The Netherlands), which also ensures concealed treatment allocation. Stratification will be performed for center and whether or not a patient is included with a minor amputation.

### 7.3 Study procedures

Patients from each (remaining) study arm will be monitored up to 36 months after randomisation. At the start of the trial, patients' baseline characteristics will be obtained. Pain scores will be collected through first phase of the trial. Questionnaires will be completed at baseline and will be sent to the patients' home after 3 months and 1 year.

Amputation rate, ulcer recurrence, additional interventions, mortality, adverse events and costs will be monitored after 1 year and 3 years.

Assessment	Before randomisation	Week 1-8, once a week	After 3 months	After 1 year	After 3 years
Patient characteristics	*				
Meggitt-Wagner classification	*		*	*	
Wound measurements	*				
Ankle blood pressure	*		*	*	
Toe systolic pressure	*		*	*	
TcPO2	*		*	*	
VAS		*	*	*	
Freedom of amputation			*	*	*
Complete ulcer healing			*	*	*
Recurrent ulcer			*	*	*
Nr of additional vascular events		*	*	*	*
Adverse events		*	*	*	
Patient's out of pocket expenses			*		
Questionnaires	*		*	*	*

*Table 1 Assessments and follow-up*

#### 7.4 Withdrawal of individual subjects

Subjects can leave the study at any time for any reason if they wish to do so without any consequences. The (local) investigator can decide to withdraw a subject from the study for urgent medical reasons.

#### 7.5 Replacement of individual subjects after withdrawal

Subjects who withdraw from the study will not be replaced. We already adjust the sample size for an anticipated loss to follow-up of 10% in the sample-size calculation to keep sufficient power.

#### 7.6 Follow-up of subjects withdrawn from treatment

Patients who withdraw from the study for any reason will not be followed conform ethical and legal protocols. They may continue their regular treatment (including HBOT if desired) follow-up moments.

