### **4.4 Sample size calculation**

The primary outcome is the probability of amputations after 12 months. The meta-analysis showed a 15% difference (11% vs. 26%; Brouwer 2020) of amputations between patients treated with HBOT and patients treated conservatively. The sample size calculation is based on a one-sided type I error of 5% and a power of 90% to control for a type 2 error. A

generalization of the power requirements for testing multiple active treatments to one control group was used as proposed by Dunnett (Dunnett 1984).

The critical values for continuation of a treatment arm are odds ratios of 0.76 and 0.352, which are in accordance with a drop in amputations from 26% to 21% and to 11%. If the difference is <5% the HBOT treatment arm is deemed futile, while a difference of 15% or higher is deemed superior. Based on these critical values the required number of patients in each group in each stage is 68, leading to a required maximum number of 544 patients. The sample size calculation is based on a generalization of Whitehead and Jaki (Whitehead 2009, Jaki 2019). Taking into account a possible loss to follow-up of 5%, we will need a total of (up to) 573 patients.

This leads to the following stopping rules and possible scenarios after the interim analysis (using the chi-square test for differences in percentages between the groups) (see figure 2 below):

- 1) If one of the HBOT treatment groups leads to a significantly less than 5% improvement in amputation rate as compared to controls (based on the expected 26% vs 21% difference, i.e. an OR of 0.76), then this treatment group will be discontinued as it is futile.
- 2) IF a HBOT treatment group proves to decrease amputation rate significantly by >15% (26% vs 11%; OR: 0.352) as compared to controls, then superiority of a treatment arm is proven and the trial will be discontinued as it has reached its aim. If more than one HBOT-treatment arm shows this superiority, the group with the lowest number of HBOT treatments is deemed superior.
- 3) If the HBOT group(s) show(s) minor improvements in amputation rate (between 5% and 15%) over control, then these groups will continue in the second stage of the trial.

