## 9. STATISTICAL ANALYSIS

All analyses will be conducted according to the intention-to-treat principle. Baseline characteristics are summarized with descriptive statistics. Differences between dichotomous variables (like the amputation rate) will be expressed as a risk differences and Numbers Needed to Treat or Harm. Statistical precision will be expressed as 95% confidence intervals. Differences between continuous variable will be expressed as difference in means. If outcome parameters are unevenly distributed, they will be expressed as medians and inter-quartile ranges.

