### 9.1 Primary study parameters

At the interim analysis, statistical analyses of the differences in amputation rates between the study arms will be conducted using the Chi-square statistic.

At the final analysis, major amputation rates and AFS will also be estimated using Kaplan-Meier survival analysis and differences between the groups will be analysed using the log-rank test.

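### Section 7.6 ends follow-up for every withdrawal without separating stopped HBOT, investigator withdrawal and withdrawn consent, so 12-month outcomes can be lost for patients who still consent

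*Protocol*

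**What the plan says.** Protocol section 7.4 gives two ways out of the study. The patient may choose to go: "Subjects can leave the study at any time for any reason if they wish to do so without any consequences". The investigator may also act: "The (local) investigator can decide to withdraw a subject from the study for urgent medical reasons". The second route is withdrawal from the study, not only from treatment, and it does not depend on the patient withdrawing consent.

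Section 7.6 is headed as a rule for patients withdrawn from treatment, but its text is about leaving the study: "Patients who withdraw from the study for any reason will not be followed conform ethical and legal protocols". It continues: "They may continue their regular treatment (including HBOT if desired) follow-up moments". It does not provide for collecting amputation or vital status afterwards.

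The analysis depends on those outcomes:

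- Section 7.1.1 defines the main endpoint: "Major amputation rate (above ankle) and (major) amputation-free survival after 12 months of follow-up".
- Section 9 sets the analysis principle: "All analyses will be conducted according to the intention-to-treat principle".
- Section 9.1 says that at the final analysis "major amputation rates and AFS will also be estimated using Kaplan-Meier survival analysis", with the log-rank test for group differences.

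**The concern.** Three different situations fall under one rule: a patient stops HBOT sessions but is willing to be followed, the investigator removes a patient on medical grounds, or a patient withdraws consent to data collection. Only the third requires data collection to end. Because section 7.6 does not distinguish them, a centre that follows it literally may stop recording outcomes for patients who never objected to being followed.

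An intention-to-treat analysis of 12-month amputation and amputation-free survival needs both outcomes for everyone randomised. The log-rank comparison also assumes that patients censored at a given time have the same later risk as those who remain. That is doubtful for someone removed for an urgent medical reason. A statistical analysis plan can describe how missing outcomes are handled, but it cannot restore data that the protocol told centres not to collect.

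**Working it through.** **The plan's own figures.** Section 4.4 gives 68 patients × 4 groups × 2 stages = 544. Allowing for 5% loss, 544 / 0.95 = 572.6, rounded up to 573, which reproduces the stated total. Section 7.5 instead says that 10% loss was allowed for; that would give 544 / 0.90 = 604.4, so 605. The two statements disagree, but both 5% and 10% are the protocol's own figures for loss, and I use them below.

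**Timing.** Section 5.1 gives 3 to 5 sessions a week.

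- Shortest course: 20 sessions / 5 per week = 4 weeks.
- Longest course: 40 sessions / 3 per week = 13.3 weeks.

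Section 9.3 says that most amputations occur within three months. The HBOT course therefore overlaps the period of highest risk, and a patient who leaves during it may do so before the event.

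**Illustration of bias.** The documents give no withdrawal rate by arm and no amputation risk for withdrawn patients, so these inputs are assumptions:

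- No true effect, with 26% amputations in both arms (the control rate in section 4.4).
- A fraction *w* of one HBOT arm lost, and none of the control arm.
- Amputation risk *r* in those lost, who contribute nothing to the observed rate.

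Observed rate = (0.26 − *w* × *r*) / (1 − *w*).

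| *w* | *r* | Observed rate | Apparent benefit |
|---|---|---|---|
| 5% | 50% | (0.26 − 0.025) / 0.95 = 24.7% | 1.3 points |
| 10% | 50% | (0.26 − 0.050) / 0.90 = 23.3% | 2.7 points |
| 10% | 78% (three times 26%) | (0.26 − 0.078) / 0.90 = 20.2% | 5.8 points |
| 15% | 60% | (0.26 − 0.090) / 0.85 = 20.0% | 6.0 points |

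**Against the 5-point futility limit of section 4.4.** With 5% loss the limit cannot be reached even if every lost patient had an amputation: (0.26 − 0.05) / 0.95 = 22.1%, a shift of 3.9 points. With 10% loss in one arm, reaching 5 points needs *r* = 0.26 + 0.05 × 0.90 / 0.10 = 71%. The 15% row exceeds both of the protocol's loss figures.

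**Direction.** If the 10% loss at 50% risk falls in the control arm instead, the control rate reads 23.3% against 26% with HBOT, an apparent harm of 2.7 points. If both arms lose the same fraction at the same risk, the shifts cancel.

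**The case against.** **Who is covered.** The sentence in section 7.6 speaks of patients who withdraw, and section 7.4 words patient choice and investigator decision separately, so the rule might be meant for patient-initiated exits only. This reading is possible. It does not clear the text: investigator-withdrawn patients would then have no follow-up rule, and patient-initiated exits would still not be divided into stopping treatment and refusing further data collection.

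**Stopping sessions.** A reader might infer that abandoning HBOT removes a patient from the study, and hence that the HBOT arms must lose more patients than control. No section says so. Only the heading of 7.6 mentions treatment, and the text allows HBOT after exit. The link is an ambiguity to remove, not a stated rule.

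**Intention-to-treat.** A reader might say that 7.6 contradicts section 9. It does not forbid analysis by allocated group. It can remove the outcomes that such an analysis needs, which undermines the principle without contradicting it.

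**Direction.** It is tempting to conclude that the bias favours HBOT. The documents do not support this. Section 1 says that HBOT is reimbursed for this indication, and 7.6 lets those who leave receive it, so controls may leave to obtain it.

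**The earlier trial.** A reader might take the gap in section 1 between the intention-to-treat and per-protocol reductions (10% and 17%) as a guide to size. It compares two analysis sets and does not measure bias from ended follow-up.

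**The arithmetic.** It deletes withdrawn patients entirely, whereas Kaplan-Meier keeps their time and any event before exit. The table is therefore only a rough guide to the final analysis. It is also right that data collection should end when consent to it is withdrawn, and the consent documents, which are not shown, may say more.

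**Conclusion.** The point holds as a defect in the follow-up rule. Sections 7.4 and 7.6, read together, allow 12-month amputation and survival outcomes to be lost for patients who still consent, and no other section limits this. The consequences are a weakened intention-to-treat analysis and potentially informative censoring in the Kaplan-Meier and log-rank analysis. The overlap of the HBOT course with the first three months makes this more than a formality.

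The size and direction of bias are unknown. Under the stated assumptions (no true effect, loss in one HBOT arm only, 50% risk in those lost), the shift is about 1.3 points at 5% loss and 2.7 points at 10%. Passing the 5-point futility limit takes more extreme inputs, such as a risk above 71% at 10% loss. Control-arm losses would push the other way. The case for changing the text rests on the preventable loss of primary outcome data, not on a predicted false benefit. A larger sample would not remove bias from informative loss.

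**What to change.** Reword sections 7.4 and 7.6 as follows:

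- Patients who stop HBOT, or whom the investigator withdraws for medical reasons, stay in follow-up for major amputation and death to 12 months and are analysed as randomised.
- Follow-up ends only when the patient withdraws consent to further data collection.
- Patients who withdraw that consent are asked for permission to obtain amputation and vital status from records.
- The heading of 7.6 is made to match its content.

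This concerns data collection only and changes no treatment rule. The cost is protocol and consent wording plus record checks for a small number of patients. The change should be made early, because outcomes that were not collected may not be recoverable later.
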